11.4.2 Secondary Efficacy Endpoints

The proportion of subjects with acne scars and marks improved with respect to baseline and, at the same time, without any new facial acne scars after 2 and 8 weeks of treatment (treatment success) will be described using number (N) and percentage (%). The improvement of acne scars and marks will be assessed as the change of at least one grade in the qualitative Scar Global Assessment (SGA) by Goodman and Baron between baseline and Week 2 and 8. The number of new acne scars will be assessed by count after 2 and 8 weeks and comparison with baseline. The proportion of treatment successes will be compared to a referent proportion (50%, Null hypothesis proportion) using the exact binomial test.

The proportion of subjects at week 2, 4 and 8 of treatment, without any new facial acne lesions with respect to baseline (Visit 1) will be described using number (N) and percentage (%); the proportion of treatment successes will be compared to a referent proportion (50%, Null hypothesis proportion) using the exact binomial test.

Acne severity after 2, 4 and 8 weeks of treatment will be assessed through the IGA. Changes from baseline will be compared using Wilcoxon signed rank-sum test.

The improvement of skin roughness will be assessed on a 4-point scale from 0 (none; very smooth) to 3 (severe; very rough). Changes from baseline will be compared using Wilcoxon signed rank-sum test.

Skin texture change will be assessed on a 6-point scale from 0 (worse) to 5 (complete improvement), after 2, 4 and 8 weeks of treatment and it will be summarized through the number (N) and the proportion of subjects (%) for each item.

The number of applications will be self-reported by the subject to assess adherence to treatment.

Subject's and Investigator's global evaluation on performance of the study product obtained at the end of the study (Visit 4) by means of a 7-items scale will be summarized through number (N) and proportion of subjects (%) for each item.

Subject's evaluation of overall acceptability with treatment, obtained by means of a 5-item scale will be summarized through number (N) and the proportion of subjects (%) for each item.

The secondary endpoints will be described from Table 14.2.2.1 to Table 14.2.2.8.

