5.2 Secondary Objectives and Endpoints

The secondary objectives of this clinical investigation are:

- To evaluate the performance of PAPIX ACNE SCAR in the prevention and improvement of acne scars after 2 and 8 weeks of treatment. This endpoint will be assessed as the proportion of subjects with improved acne scars and marks with respect to baseline and, at the same time, without any new facial acne scars after 2 and 8 weeks of treatment. The improvement of acne scars and marks will be assessed as the change in the qualitative Scar Global Assessment (SGA) by Goodman and Baron (2006) [26] between baseline and Week 2 and 8. The number of acne scars, to identify any new scars, will be assessed through the scars count and comparison with baseline.
- To evaluate the performance of PAPIX ACNE SCAR in the prevention of acne lesions after 2, 4 and 8 weeks of treatment. The number of acne lesions, to identify any new lesions, will be assessed through the lesions count and comparison with baseline.
- To evaluate the improvement in acne severity after 2, 4 and 8 weeks of treatment, through the Investigator Global Assessment, ranging from 0 (clear; clear skin with no lesions) to 4 (severe; many inflammatory and non-inflammatory lesions).
- To evaluate the improvement of the skin roughness on a 4-point scale from 0 (none; very smooth) to 3 (severe; very rough) after 2, 4 and 8 weeks of treatment.
- To evaluate the improvement of the skin texture on a 6-point scale from 0 (worse) to 5 (complete improvement), after 2, 4 and 8 weeks of treatment.
- To evaluate the subject's adherence to treatment by the product accountability and information asked to the subject.
- To evaluate the subject's and Investigator's global evaluation of satisfaction with regards to the performance of PAPIX ACNE SCAR, through a specific questionnaire.
- To evaluate the subject's overall acceptability of the treatment, through a specific questionnaire.

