7. SAMPLE SIZE AND STATISTICAL POWER CONSIDERATION

An exact binomial test with a nominal 5% two-sided significance level has 80% power to detect the difference between the Null hypothesis proportion, π_0 of 0.5 (i.e., 50% of subjects with treatment success) and the Alternative

proportion, π_1 , of 0.75 (i.e., 75% of subjects with treatment success) when the sample size is 30 subjects. Assuming a possible 25% dropout rate, 40 subjects were enrolled, according to the CIP provisions.

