9. GENERAL ISSUES FOR STATISTICAL ANALYSIS

9.1 Definitions, Derived Variables and Datasets

Variable	Туре	Description
lesion_num	Continous	Number of lesions
scar_num	Continous	Number of scars
srorres_iga	Discrete	Investigator's Global Assessment: 0 = Clear skin 1 = Almost clear skin 2 = Mild severity 3 = Moderate severity 4 = Severe
srorres_sga	Discrete	Scar Global Assessment: 0 = Clear skin 1 = Almost clear skin 2 = Mild severity 3 = Moderate severity 4 = Severe
srorres_rough	Discrete	Skin roughness assessment:0 = None, very smooth1 = Mild, slightly rough2 = Moderate, rough3 = Severe, very rough
srorres_texture	Discrete	Skin texture assessment: 0 = worse 1 = slightly worse 2 = no change 3 = slightly improved 4 = improved

		5 = complete improvement
qsorres_perf_subj	Discrete	Subject's global evaluation of performance: 1 = Very much improved 2 = Improved 3 = Minimally improved 4 = No change 5 = Minimally worse 6 = Worse
qsorres_perf_inv	Discrete	7 = Very much worseInvestigator's global evaluation of performance:1 = Very much improved2 = Improved3 = Minimally improved4 = No change5 = Minimally worse6 = Worse7 = Very much worse
qsorres_satisf	Discrete	Subject's overall acceptability: 1 = Very much satisfied 2 = Satisfied 3 = Neither satisfied nor dissatisfied 4 = Dissatisfied 5 = Very much dissatisfied
ecoccur	Discrete	Compliance
ecdur	Continous	Treatment skipped times
aeterm	Discrete	Adverse event description

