11.5 Summary of Efficacy Analyses

Endpoint	Analysis	Populations
Proportion of subjects with improved acne scars and marks at week 4 of treatment (Visit 3) and, at the same time, without any new facial acne scars with respect to baseline (Visit 1).	Exact binomial test	FAS PP
Proportion of subjects with improved acne scars and marks at week 2 and 8 of treatment (Visits 2 and 4) and, at the same time, without any new facial acne scars with respect to baseline (Visit 1).	Exact binomial test	FAS
Proportion of subjects at week 2, 4 and 8 of treatment, without any new facial acne lesions with respect to baseline (Visit 1).	Exact binomial test	FAS
Change from baseline (Visit 1) to each time point (Visit 2, 3 and 4) in the acne severity, according to the Investigator Global Assessment.	Wilcoxon signed rank- sum test	FAS
Change from baseline (Visit 1) to each time point (Visit 2, 3 and 4) in the skin roughness, on a 4-point scale from 0 (none; very smooth) to 3 (severe; very rough).	Wilcoxon signed rank- sum test	FAS
Change from baseline (Visit 1) to each time point (Visit 2, 3 and 4) in the skin texture on a 6-point scale from 0 (worse) to 5 (complete improvement).	Number (N) and the proportion of subjects (%) for each item	FAS
Subject's and Investigator's global evaluation on performance of the study product at the end of the study (Visit 4) by means of a 7-items scale.	Number (N) and the proportion of subjects (%) for each item	FAS
Subject's overall acceptability of the treatment at the end of the study (Visit 4) by means of a 5-item scale.	Number (N) and the proportion of subjects (%) for each item	FAS

Subject's adherence to treatment by the product accountability.	Mean percentage within each treatment group	FAS
---	---	-----

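### The 50% reference used to test the no-new-lesions proportion is not a no-effect value, because a subject whose lesion count is unchanged is scored as a success

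*SAP*

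**What the plan says.** SAP 11.4.2 gives the lesion endpoint at Weeks 2, 4 and 8 as the proportion "without any new facial acne lesions with respect to baseline (Visit 1) will be described using number (N) and percentage". It calls these subjects treatment successes and applies the rule "The proportion of treatment successes will be compared to a referent proportion (50%, Null hypothesis proportion) using the exact binomial test". The same rule is used there for the scar composite at Weeks 2 and 8. The summary table in SAP 11.5 assigns the exact binomial test to "Proportion of subjects at week 2, 4 and 8 of treatment, without any new facial acne lesions with respect to baseline (Visit 1").

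Protocol 5.2 says how a new lesion is found: "The number of acne lesions, to identify any new lesions, will be assessed through the lesions count and comparison with baseline". The only lesion variable in SAP 9.1 is lesion_num, described as "Number of lesions". No lesion-level variable is listed.

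The 50% comes from the sample size in SAP section 7: "An exact binomial test with a nominal 5% two-sided significance level has 80% power", with a null of "50% of subjects with treatment success" and an alternative of "75% of subjects with treatment success) when the sample size is 30 subjects". SAP 11.4.1 uses it for the primary composite, which requires a change of at least one SGA grade and no new scars. Neither document justifies 50% for lesions or gives an untreated rate. The protocol synopsis plans only N (%) for the lesion proportion, and protocol 7.3.5.2 names no test for it.

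**The concern.** The composite and the lesion endpoint treat the unchanged subject in opposite ways. In the composite, an unchanged SGA grade is a failure. In the lesion endpoint, an unchanged count means no new lesions and is a success. Carrying the 50% from one to the other credits every subject who merely stays the same.

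Prevention of lesions is a stated secondary objective and a property claimed for the device, and the study is meant to support the CE mark. A p-value below 0.05 against 50% would be read as evidence of prevention. Under the count definition it can arise from subjects whose acne did not change.

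**Working it through.** **Inputs.** From SAP section 7: exact binomial test, two-sided 5%, null 0.50, alternative 0.75, n = 30, and 40 enrolled after allowing 25% dropout. Missing data are not replaced (SAP 9.1.4), so n = 30 and n = 40 are used as the planned evaluable and enrolled numbers. Turnover, tie rates and drift are assumptions.

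**Step 1: reproduce the plan's figure.** At n = 30 the test rejects upward at 21 or more successes (two-sided p = 0.043). Power at 0.75 is 80.3%, and 30/(1 − 0.25) = 40, both as stated. At n = 40 the cut-off is 27 (two-sided p = 0.038). At a true 50%, upper-tail rejection is 2.1% (n = 30) and 1.9% (n = 40).

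**Step 2: success rate with no effect.** Success is a count that has not risen. If rises and falls are equally likely, each has probability (1 − P(tie))/2. Then P(success) = P(fall) + P(tie) = (1 + P(tie))/2, which equals 50% only if no subject ever ties.

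**Step 3: size.** Assume the same mean number of lesions appears and resolves per subject, each Poisson. The change is then Skellam with equal means. P(declared above 50%) is the exact binomial upper tail at the resulting success rate.

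| Assumed mean turnover | P(tie) | No-effect success | n = 30 | n = 40 |
|---|---|---|---|---|
| 1 | 31% | 65% | 38% | 46% |
| 2 | 21% | 60% | 19% | 22% |
| 3 | 17% | 58% | 13% | 15% |
| 5 | 13% | 56% | 9% | 10% |
| 10 | 9% | 54% | 6.2% | 6.6% |
| 20 | 6% | 53% | 4.6% | 4.7% |
| 50 | 4% | 52% | 3.5% | 3.5% |

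By tie share directly: 10% ties give (1 + 0.10)/2 = 55% success and rejection of 6.9% (n = 30) or 7.5% (n = 40). With 40% ties, success is 70% and rejection 59% or 70%.

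**Step 4: an example.** Of 30 subjects, 12 have the same count, 9 fewer lesions and 9 more. Successes are 12 + 9 = 21, p = 0.043 in the product's favour, although rises equal falls.

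**Step 5: drift.** With an assumed mean of 20 and a 10% fall unrelated to the gel, success is 66% and rejection 39% (n = 30) or 48% (n = 40). With means of 3 appearing and 2 resolving, success is 41% and upward rejection about 0.1%.

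**Step 6: the other reading of a new lesion.** Suppose any newly arisen lesion counts, with a constant hazard and an assumed event-free rate of 50% at Week 4 for an inert product. The rate is then 0.5^0.5 = 71% at Week 2 and 0.5^2 = 25% at Week 8. That product would be declared above 50% at Week 2 with probability 62% (n = 30) or 74% (n = 40), and below 50% at Week 8 with probability 80% or 90%. One reference cannot be the no-effect value at all three visits.

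**The case against.** Several objections have force.

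- **Size.** The large figures need low turnover. Entry requires IGA 2 or 3, described in protocol 6.4.3 as from some to many non-inflammatory lesions. With mean turnover of 10 to 50 the rate is 6.6% down to 3.5%, modest though still above 2%. This stands, and is why the whole range is shown.
- **Direction.** A reader might infer that an inert product will generally be declared effective, however lesions are counted. The documents do not support that. The mechanism belongs to the count definition and to symmetric fluctuation. Subjects must be off other acne treatments, so counts could drift upward and the test become conservative. Under the newly-arisen reading, a subject with a stable count but turnover is a failure and the bias can reverse. What survives every reading is that 50% has no justification as a no-effect value.
- **A performance goal.** The 50% might be a target rather than a no-effect rate. The SAP labels it the null hypothesis proportion and gives no rationale for it as a lesion target.
- **A better test.** A reader might infer that testing change in the count against zero would show prevention. It removes only the credit for ties. With the 10% fall of Step 5, simulated Wilcoxon signed-rank rejection in the improvement direction is about 40% (n = 30) and 50% (n = 40), much like the binomial test. The study has no control arm and supplies a cleanser to every subject.
- **Weight.** This is an unadjusted secondary endpoint. The primary composite does not credit an unchanged SGA grade and is not affected by this mechanism.

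**Conclusion.** The point holds in limited form. Under the count definition that protocol 5.2 and SAP 9.1 support, an unchanged subject is a success, so 50% is not the success rate of an ineffective product. With symmetric fluctuation the no-effect rate is above 50% whenever ties can occur. The false-positive chance at each visit then lies between about 3.5% and 38% (n = 30) or 46% (n = 40), against about 2% nominal. Where it falls in that range depends on turnover, which the documents do not give; downward drift raises it and upward drift lowers it. The three p-values should not be used as evidence of lesion prevention. This should be corrected, but it does not touch the primary analysis.

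**What to change.** In SAP 11.4.2, SAP 11.5 and Table 14.2.2.2, delete the exact binomial test against 50% for the lesion endpoint. Report N (%) at Weeks 2, 4 and 8 as descriptive, with a confidence interval if wanted. This returns the analysis to the protocol synopsis.

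If a test is wanted, analyse the within-subject change in lesion_num against zero under the protocol 7.3 rule for continuous variables: paired t-test, with the Wilcoxon signed-rank test also done if the data are not normal. Record it in SAP section 13 as an added analysis.

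In either case, state that neither the proportion nor the change from baseline separates a product effect from spontaneous change or from the supplied cleanser in this uncontrolled study.

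The cost is SAP wording and one table. The three lesion proportions lose their p-values, and no new data are needed.

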Secondary study endpoints	
Performance endpoints
 
 - Proportion of subjects with improved acne scars and marks at week 2 and 8 of treatment (Visits 2 and 4) and, at the same time, without any new facial acne scars with respect to baseline (Visit 1). - Proportion of subjects at week 2, 4 and 8 of treatment, without any new facial acne lesions with respect to baseline (Visit 1). - Change from baseline (Visit 1) to each following time point in the acne severity, according to the Investigator Global Assessment. - Change from baseline (Visit 1) to each following time point in the skin roughness, on a 4-point scale from 0 (none; very smooth) to 3 (severe; very rough). - Change from baseline (Visit 1) to each following time point in the skin texture on a 6-point scale from 0 (worse) to 5 (complete improvement). - The subject's adherence to treatment by the product accountability; - The subject's and Investigator's global evaluation of satisfaction with regards to the performance of PAPIX ACNE SCAR, through a specific questionnaire. - To evaluate the subject's overall acceptability of the treatment, through a specific questionnaire. 
Safety endpoints
 
 1. Number and type of adverse events (AEs) occurring during the study (seriousness, severity, and relation to study treatment) 2. Local tolerability at the site of application.
Sample size determination	An exact binomial test with a nominal 5% two-sided significance level will have 80% power to detect the difference between the Null hypothesis proportion, π_0 of 0.5 (i.e., 50% of patients with treatment success) and the Alternative proportion, π_1 , of 0.75 (i.e., 75% of patients with treatment success) when the sample size is 30 subjects. Assuming a possible 25% dropout rate, 40 subjects will be enrolled.

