6.4 Procedures

6.4.1 Study Visits and Assessments

Visit 1 screening – baseline- treatment start (day 1):

Subjects will be evaluated with regard to the inclusion and exclusion criteria that will allow their participation into the study.

Before any study specific evaluation is carried out, subjects will receive all the information about the study by the Investigators and will sign an informed consent form. In the case of minors, the informed consent form shall be signed by the parents or the guardian.

The following activities will be performed:

- Collection of information about demography
- Medical and surgical history
- Acne medical history (duration, previous treatments)
- Physical examination (only dermatologic)
- Face cutaneous examination:
 - type of skin (dry/normal/oily)
 - site of acne lesions (on the face) and count
 - acne scars count
 - acne scars global assessment by the SGA
 - acne global assessment by IGA
 - roughness and skin texture evaluations
- Photographs of the face
- Previous (in the 6 months before) and concomitant medications/treatments recording
- Inclusion/exclusion criteria assessment
- Study product delivery to subject and instructions on how to use it
- Recommendations for face cleaning to follow.

Recommendations for face cleaning to follow: throughout the study subjects will be required to avoid soap and use only the product Papix cleanser for their face. The product will be provided by the Sponsor of the study. No other cleanser other than the product provided by the Investigator will be permitted.

PAPIX ACNE SCAR application: apply twice a day for 8 weeks, 2 FTU (finger tip units) in the morning and in 2 FTU the evening before bedtime, on the face, and massaged gently into the skin until absorbed.

Visits 2 and 3 – follow-up (Day 14 ± 3 and 28 ± 3, respectively):

The following activities will be done at visit 2 and 3:

- Face cutaneous examination:
 - acne scars and lesions count
 - acne scars global assessment by the SGA
 - acne global assessment by IGA
 - roughness and skin texture evaluations
- Photographs of the face
- Changes in concomitant medications/treatments recording
- Study product collection and new delivery to subject (only at visit 3)
- Treatment adherence check with the subject
- Recommendations for face cleaning to follow
- Adverse events (occurred since previous visit) recording.

Visit 4 – End of treatment and end of study (Day 56 ±3):

The following activities will be done at visit 4:

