7.3.5.2 Secondary endpoints

The prevention and improvement of acne scars after 2 and 8 weeks of treatment will be assessed as the difference from baseline and analysed using paired t-test. The number of new scars will be assessed by count and comparison with baseline. The improvement of acne scars and marks will be assessed as the change of at least one grade in the qualitative Scar Global Assessment (SGA) by Goodman and Baron [26] between baseline and Week 2 and 8.

The number of new lesions will be assessed by count after 2 and 8 weeks and comparison with baseline.

Acne severity after 2, 4 and 8 weeks of treatment will be assessed through the IGA. Changes from baseline will be compared using Wilcoxon signed rank-sum test.

The improvement of skin roughness will be assessed on a 4-point scale from 0 (none; very smooth) to 3 (severe; very rough). Changes from baseline will be compared using Wilcoxon signed rank-sum test.

Skin texture change will be assessed on a 6-point scale from 0 (worse) to 5 (complete improvement), after 2, 4 and 8 weeks of treatment and it will be summarized through the number (N) and the proportion of patients (%) for each item.

The number of applications will be self-reported by the subject and the product accountability will be summarized to assess adherence to treatment.

Subject's and Investigator's global evaluation on performance of the study product obtained at the end of the study (Visit 4) by means of a 7-items scale will be summarized through number (N) and proportion of patients (%) for each item.

Subject's evaluation of overall acceptability with treatment, obtained by means of a 5-item scale will be summarized through number (N) and the proportion of patients (%) for each item.

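### The endpoint of no new facial acne lesions at weeks 2, 4 and 8 is to be judged from lesion counts against baseline, which give new minus resolved lesions and cannot show that none appeared

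*SAP*

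**What the plan says.** The endpoint is the protocol's own. The synopsis lists it as "Proportion of subjects at week 2, 4 and 8 of treatment, without any new facial acne lesions with respect to baseline (Visit 1" and SAP 5.2, 11.4.2 and 11.5 carry it over; in SAP 11.4.2 it reads "The proportion of subjects at week 2, 4 and 8 of treatment, without any new facial acne lesions with respect to baseline (Visit 1". SAP 11.4.2 adds a test, worded alike for the scar and lesion endpoints: "The proportion of treatment successes will be compared to a referent proportion (50%, Null hypothesis proportion) using the exact binomial test".

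The method for finding a new lesion is in the protocol. Section 5.2 says: "The number of acne lesions, to identify any new lesions, will be assessed through the lesions count and comparison with baseline". Section 7.3.5.2 repeats it but names two of the three visits: "The number of new lesions will be assessed by count after 2 and 8 weeks and comparison with baseline". The lesion paragraph of SAP 11.4.2 gives no derivation; the sentence there about counting concerns scars.

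On the data, Protocol 6.4.1 lists at Visit 1 "site of acne lesions (on the face) and count", and at Visits 2, 3 and 4 only "acne scars and lesions count". SAP 9.1 describes the lesion variable as "Number of lesions". Face photographs are taken at every visit, but no section uses them to identify new lesions. The CRF (version 1.0, SAP 1.3) is not among the documents.

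**The concern.** The endpoint asks whether any lesion has appeared since Visit 1. A total answers a different question: whether more lesions are present than before. The two agree only if no baseline lesion resolves, and the plan itself expects lesions to resolve. Improvement in acne severity is an objective, and the IGA scale in Protocol 6.4.3 runs down to skin with no lesions.

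This endpoint has no second condition that would limit the error, and it is tested at three visits. It carries the objective of lesion prevention in SAP 3.2, in a study meant to support the CE mark of a device described as preventing new lesions (Protocol sections 2 and 3). If totals are compared, a proportion significantly above 50% describes the balance of new and resolved lesions and would be reported under a label that says something stronger.

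**Working it through.** **The plan's own figure.** SAP 7 gives 80% power for the primary endpoint at n = 30, 0.50 against 0.75, two-sided 5%. Under 0.50, P(X ≥ 21 of 30) = 0.0214, so the two-sided p is 0.043; 20 of 30 gives 0.099. Success therefore needs 21 of 30. Under 0.75, P(X ≥ 21) = 0.803, so the stated 80% reproduces. Enrolment is 30 / (1 − 0.25) = 40. With all 40 evaluable, 27 successes are needed (p = 0.038; 26 gives 0.081). The plan states no power for the lesion endpoint. The same test and limits are used below.

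**The identity.** Let T1 be the Visit 1 total, R the baseline lesions resolved by the visit, and N the new lesions present. The follow-up total is T1 − R + N, so follow-up minus baseline is N − R. A rise proves N ≥ 1. No rise proves only N ≤ R. For example, 20 at baseline, 8 resolved and 3 new gives 20 − 8 + 3 = 15: the subject passes with 3 new lesions. A subject with N = 0 can never show a rise. With accurate counts, every misclassification is therefore a false success.

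**Possible size.** The documents give no baseline count, resolution rate or rate of new lesions, so these inputs are assumed. The pass rule (follow-up total ≤ Visit 1 total) is inferred from the count comparison. Take B lesions at baseline, R ~ Binomial(B, q) and N ~ Poisson(λ), independent. Then:

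- true proportion with no new lesion = exp(−λ)
- proportion passing = Σ over r of P(R = r) × P(N ≤ r)
- chance of a significant result above 50% = P(X ≥ 21 of 30) or P(X ≥ 27 of 40) at the passing proportion

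| B | q | λ | Truly none new | Pass by count | Significant, n = 30 | Significant, n = 40 |
|---|---|---|---|---|---|---|
| 20 | 10% | 1 | 36.8% | 82.5% | 97% | 99% |
| 20 | 30% | 4 | 1.8% | 81.2% | 96% | 99% |
| 20 | 30% | 8 | 0.03% | 34.0% | about 0 | about 0 |
| 20 | 30% | 12 | under 0.001% | 8.1% | about 0 | about 0 |
| 20 | 50% | 4 | 1.8% | 98.2% | over 99% | over 99% |
| 20 | 50% | 8 | 0.03% | 76.1% | 84% | 92% |
| 20 | 50% | 12 | under 0.001% | 36.7% | about 0 | about 0 |
| 10 | 50% | 8 | 0.03% | 22.4% | about 0 | about 0 |
| 30 | 50% | 8 | 0.03% | 96.8% | over 99% | over 99% |

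If nothing resolves (q = 0), the passing proportion equals exp(−λ) and the rule is exact. In the first row the true proportion lies below the 50% reference, yet the count rule would very probably give a significant result above it.

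**The case against.** The strongest reply is that the flaw depends on a form nobody can see here. The CRF may record new lesions at each visit, and the SAP variable list is not complete. Protocol 7.3.5.2 can also be read as counting the new lesions themselves, and no section writes down the rule of follow-up total at or below baseline. This stands as a limit on certainty. A reader might infer that the CRF has no new-lesion item; the documents do not show that. They do show a stated count method and a listed total, with no text linking the endpoint to anything else, so a SAP edit is needed either way.

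The photographs might also allow new lesions to be identified. The documents do not say whether they are adequate, and such a reading would itself need a written derivation.

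The figures are not evidence about this trial. That is right. A reader might infer that the test is bound to succeed, but several rows of the table fail almost surely. Only the direction is established.

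Finally, this is one secondary endpoint in an uncontrolled study, and without a control even perfect data could not attribute an absence of new lesions to the device. That limits the consequence but does not repair the label: the proportion is wrong as a description if totals are used.

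**Conclusion.** The point holds for the lesion endpoint and should be fixed. Followed as written, the plan measures new minus resolved lesions, errs only towards success when counts are accurate, and tests the result against 50% at weeks 2, 4 and 8. How large the error is in this trial cannot be known from the documents. Under the assumed inputs it ranges from small (8% passing where almost none qualify) to nearly complete (98% passing where about 2% qualify). The conclusion rests on lesions resolving between visits and on no separate record of new lesions being used.

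A reader might extend this to the scar component of the primary composite, which SAP 11.4.1 also assesses by count against baseline. The documents do not support that as a defect. It would arise only if scars leave the count by the visit. SGA grade 1 treats flat marks as scars (Protocol 6.4.2), but no section says whether they are counted. That is a point to clarify. The sample size is unaffected.

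**What to change.** Before database lock, check the CRF for an item recording new lesions at each visit.

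- **If there is one:** derive the endpoint from it and write the derivation, for all three visits, in SAP 9.1 and 11.4.2.
- **If there is none:** analyse and report the endpoint as *no increase in total lesion count from Visit 1* (follow-up total ≤ Visit 1 total) in SAP 5.2, 11.4.2, 11.5 and the title of Table 14.2.2.2. Draw no conclusion from it about absence of new lesions or about prevention. Record the change from the protocol's wording in SAP 13, which now declares no deviation, and amend the protocol if its section 9 requires it.

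For the scar component, add one sentence to SAP 11.4.1 and 11.4.2 saying how a new scar is derived and whether flat marks are counted. Leave the primary endpoint's label as it is.

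The cost is one CRF check, a few SAP edits and possibly an amendment. No collected data and no sample size change. Adding a CRF field now appears too late, since SAP 7 describes enrolment in the past tense. The real price of the second route is a weaker claim on lesion prevention.
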